17.3.1. LABORATORY REFERENCE RANGES AND MARKEDLY ABNORMAL CRITERIA

Quantitative laboratory measurements will be compared with the relevant laboratory reference ranges in SI units and categorized as:

- Low: Below the lower limit of the laboratory reference range.
- Normal: Within the laboratory reference range (upper and lower limit included).

High: Above the upper limit of the laboratory reference range.

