#### **4.3 DOSE JUSTIFICATION**

To evaluate the pharmacokinetics in Chinese healthy participants, the two Phase III doses 40 mg and 80 mg have been selected for this study. This is considered to be adequate to assess the PK of baloxavir marboxil in a Chinese healthy population and to compare the results with those from Caucasian and Japanese populations.

In the Phase I single ascending dose and multiple ascending dose placebo-controlled study conducted in Japan, baloxavir marboxil was administered to 40 healthy male adult subjects. A total of 6 adverse events were reported in 6 of the 40 randomized subjects and no serious adverse events were reported. Single oral doses of baloxavir marboxil up to 80 mg were found to be safe and well tolerated in healthy adult subjects.

In another Phase I study conducted in Japan to evaluate the relative bioavailability and food effect, 20 mg of baloxavir marboxil formulated as either a tablet or suspension was administered to 29 healthy subjects (14 subjects in the bioavailability part and 25 subjects in the food effect part of the study). In the bioavailability part of the study, 2 of 14 subjects experienced treatment-emergent adverse events of nasopharyngitis and blood uric acid increased. In the food effect part of the study, 10 of 15 subjects experienced at least 1 treatment-emergent adverse events (ALT increased occurred in more than 3 subjects) with a total of 15 treatment-emergent adverse events reported overall and no deaths, serious treatment-emergent adverse events or discontinuation due to treatment-emergent adverse events were reported in this study. In the Phase I drug-drug interaction study with CYP3A4 substrate conducted in the United States, a single dose of 5 mg of midazolam was administered alone or in combination with a single dose of 40 mg of baloxavir marboxil to 12 healthy adult subjects. Three adverse events were reported in 2 of the 12 subjects and no deaths or serious adverse events were noted. In the Phase I drug-drug interaction study in the United States, a single dose of 20 mg of baloxavir marboxil was administered alone or in combination with repeated dose of 200 mg of itraconazole to 12 healthy adult subjects.

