#### **8.3.6      Non-Serious Adverse Events of Special Interest**

Non-serious adverse events of special interest are required to be reported by the investigator to the Sponsor immediately (i.e., no more than 24 hours after learning of the event; see [Appendix 2](#) for reporting instructions).

Non-serious adverse events of special interest for this study include the following:

- Cases of an elevated ALT or AST in combination with either an elevated bilirubin or clinical jaundice, as defined in [Appendix 3](#).
- Suspected transmission of an infectious agent by the study drug, as defined below:

Any organism, virus, or infectious particle (e.g., prion protein transmitting transmissible spongiform encephalopathy), pathogenic or non-pathogenic, is considered an infectious agent. A transmission of an infectious agent may be suspected from clinical symptoms or laboratory findings that indicate an infection in a participant exposed to a medicinal product. This term applies only when a contamination of the study drug is suspected.

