**Table 6 Adverse Event Severity Grading Scale**

Severity	Description
Mild	Discomfort noticed, but no disruption of normal daily activity
Moderate	Discomfort sufficient to reduce or affect normal daily activity
Severe	Incapacitating with inability to work or to perform normal daily activity

Note: Regardless of severity, some events may also meet seriousness criteria. Refer to definition of a serious adverse event.

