## **6. ABNORMAL LIVER FUNCTION TESTS**

Drug-induced liver injury has been the most frequent single cause of safety-related drug marketing withdrawals or limitation of use, as well as discontinuation of clinical development programs. Hence, detection and reporting of liver function abnormalities that might herald a signal of severe drug-induced liver injury are conducted for any product in clinical development, irrespective of its expected liability for this risk.

The finding of an elevated ALT or AST ( $>3 \times \text{ULN}$ ) in combination with either an elevated total bilirubin ( $>2 \times \text{ULN}$ ) or clinical jaundice in the absence of cholestasis or other causes of hyperbilirubinemia is considered to be an indicator of severe liver injury. Therefore, investigators must report as an adverse event the occurrence of either of the following:

- Treatment-emergent ALT or AST  $>3 \times \text{ULN}$  in combination with total bilirubin  $>2 \times \text{ULN}$ .
- Treatment-emergent ALT or AST  $>3 \times \text{ULN}$  in combination with clinical jaundice.

The most appropriate diagnosis or (if a diagnosis cannot be established) the abnormal laboratory values should be recorded on the Adverse Event eCRF (see [Section 4](#) of this Appendix) and reported to the Sponsor immediately (i.e., no more than 24 hours after learning of the event), either as a serious adverse event or a non-serious adverse event of special interest (see [Section 5.1](#) of Appendix 2).

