17.1.1.1. Severity

Severity is classed as mild/ moderate/ severe (increasing severity). If a subject reports an AE more than once within that SOC/ PT, the AE with the worst-case severity will be used in the corresponding severity summaries.

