17.3. LABORATORY EVALUATIONS

Results from the local laboratory will be included in the reporting of this study for Hematology, Clinical Chemistry, Urinalysis, Coagulation, Thyroid Functions, Lipid Profiles. The test details can be found in Appendix 4, [Table 7](#) of the protocol.

Presentations will use SI Units.

Quantitative laboratory measurements reported as "< X", i.e. below the lower limit of quantification (BLQ), or "> X", i.e. above the upper limit of quantification (ULQ), will be converted to X for the purpose of quantitative summaries, but will be presented as recorded, i.e. as "< X" or "> X" in the listings.

In the case of a retest (same visit number assigned), the latest available measurement for that visit will be used for by-visit summaries. The following summaries will be provided for laboratory data:

- Actual and change from baseline by visit (for quantitative measurements)
- Incidence of abnormal values according to normal range criteria (for quantitative measurements)
- Shift from baseline to worst value by Investigator's Assessment

Document: Roche_YP40902_SAP

Authors: [REDACTED], [REDACTED], [REDACTED]

Version Number: 2.2

Version Date: 06MAR2020

Template No.: CS_TP_BS016 Revision 5

Reference: CS_WI_BS005

Effective Date: 01April2018

[REDACTED]

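### SAP 17.3.1 classes laboratory values only as Low, Normal or High and carries over neither the protocol's marked-abnormality tier nor its liver criterion

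*SAP*

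**What the plan says.** **SAP.** Section 17.3 plans three laboratory summaries: actual values and change from baseline by visit; "Incidence of abnormal values according to normal range criteria (for quantitative measurements"); and "Shift from baseline to worst value by Investigator's Assessment". Section 17.3.1 supplies the classes for the second. They are Low, Normal and High, with the top one defined as "High: Above the upper limit of the laboratory reference range". Nothing further is given under that title, whereas ECG (17.4.1) and vital signs (17.5.1) each have explicit markedly abnormal limits. Sections 6.5 and 17.3 take the latest retest for a by-visit summary. Section 6.5 keeps unscheduled values out of those summaries, though they count towards a worst-case value. Section 3.3 lists two changes from the protocol, both about analysis sets.

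**Protocol.** Section 8.3.6 names as events of special interest "Cases of an elevated ALT or AST in combination with either an elevated bilirubin or clinical jaundice, as defined in" Appendix 3. Section 6 of that appendix sets the limits (ALT or AST >3 × ULN, with total bilirubin >2 × ULN or with clinical jaundice) and says such a finding "is considered to be an indicator of severe liver injury". Appendix 4 adds a general second tier for all laboratory tests: a value outside a wider marked range that also shows a defined change from baseline is flagged HH or LL in the listings. Section 5.2 excludes ALT, AST or total bilirubin only above 1.5 × ULN.

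**The concern.** Safety and tolerability is the secondary objective, and protocol Table 3 names clinical laboratory tests among its endpoints. The protocol gives two ways of separating a marginal laboratory rise from an important one. The SAP uses neither, and does not record that it has set them aside. As described, its summaries would let the study report state how many participants had a High ALT at each dose, but not how many exceeded 3 × ULN or met the liver criterion. A reader could take several values just above ULN for a liver signal, or fail to see one large rise among them.

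**Working it through.** No sample-size or power figure is involved; this is a check of rules against each other.

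**1. The SAP classes against the protocol's limits.** SAP rule: High if value/ULN > 1. Protocol laboratory rule: ALT or AST > 3 × ULN and total bilirubin > 2 × ULN. Entry rule: excluded if > 1.5 × ULN. Illustrative pairs, in multiples of ULN:

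| ALT | Bilirubin | SAP class for ALT | Allowed at entry | Laboratory part of liver criterion |
|---|---|---|---|---|
| 1.05 | 0.5 | High | yes | no |
| 1.4 | 0.5 | High | yes | no |
| 2.9 | 1.0 | High | no | no |
| 3.1 | 2.1 | High | no | met |
| 10 | 4 | High | no | met |

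All five ALT values fall in one cell. The first two could be High with no change since baseline. Because each test is classed separately, the table also cannot show whether a High ALT and a High bilirubin belong to the same person.

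**2. Whether the by-visit summaries recover the peak.** They report a maximum (SAP 6.1), but in measured units, one test at a time. Protocol 8.2.4 requires clinically significant abnormal values to be repeated until they settle. If a repeat carries the same visit number, the later and probably lower value replaces the peak. If the peak itself was an unscheduled draw, it never enters. The maximum can therefore miss it.

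**3. The marked tier.** Protocol Appendix 4 requires HH/LL flags. SAP 17.3.1 has the title but no such rule, and SAP 3.3 is silent.

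**4. Which ULN.** Protocol Appendix 4 uses sponsor standard ranges in place of the investigator's, and transforms ALT, AST and total bilirubin using upper limits only. SAP 17.3 and 17.3.1 use local laboratory results and whatever laboratory range is relevant. The transformation formula is not given. If it is simple scaling (an assumption), transformed value = value × ULN(standard)/ULN(local), so the multiple of ULN is unchanged. If untransformed values were set against the standard range, the multiple would change by the factor ULN(local)/ULN(standard), which the documents do not let one compute.

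**5. What a count would allow the report to say.** If nobody met the criterion, the exact two-sided 95% upper limit is 1 − 0.025^(1/n). For n = 16 per dose this is 1 − 0.025^(1/16) = 20.6%; for all 32 it is 1 − 0.025^(1/32) = 10.9%. These limits are wide. They show what could be reported, not an error in the plan.

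**The case against.** The strongest reply is that a qualifying case should not go unreported. Appendix 3 Section 6 obliges investigators to record it as an adverse event and notify the sponsor within 24 hours, and protocol 8.2.4 has them review every laboratory report. The shift table uses the worst value, change from baseline is summarised, and protocol Table 5 requires individual listings with abnormal results flagged. With 32 participants those listings can be read by hand. The output templates are also not in the documents. All of this stands, and it limits the point to what the SAP describes. It does not supply a summary that verifies reported cases against the laboratory data: the shift depends on investigator judgement, and a case may be coded under a diagnosis.

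A reader might infer more than the documents support:

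- **That large and small rises are counted alike throughout.** This is true only of the normal-range incidence table.
- **That ALT is the only laboratory signal in the protocol.** Section 4.3 reports that "ALT increased occurred in more than 3 subjects", but also reports raised blood uric acid. The liver provision is generic: Appendix 3 Section 6 says it applies to any product in development, whatever its expected liver risk.
- **That an asymptomatic rise can grade no higher than mild,** because Table 6 defines mild as "Discomfort noticed, but no disruption of normal daily activity". Appendix 2 Section 3.1 offers Table 6 as guidance and mentions predefined grading criteria, so this does not follow.
- **That the earlier ALT rate can be projected onto these 32 participants.** It is an adverse event rate from another study, its denominator is printed as both 25 and 15, and a laboratory High count is a different quantity.
- **That leaving out a special-interest summary was an oversight.** The SAP version history records its removal as a decision.

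**Conclusion.** The point holds as a gap in the planned laboratory summaries. SAP 17.3.1 omits the marked tier that its title announces and that protocol Appendix 4 requires. No summary described in the SAP applies the Appendix 3 Section 6 criterion to the data, and SAP 3.3 does not disclose either omission. The consequence is loss of information: one cell spans everything above ULN, including values acceptable at entry, and by-visit maxima can miss a peak. The documents do not show that a serious case would go undetected, or that any particular number of raised values should be expected. This is an inexpensive improvement worth making. The conclusion assumes that the unseen templates add nothing beyond the SAP text; if they already contain these outputs, only the SAP wording needs to change.

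**What to change.** In SAP 17.3, by dose group on the safety analysis set:

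1. Tabulate each participant's worst post-dose ALT, AST and total bilirubin, including unscheduled and retest values, as multiples of ULN against baseline class. Use the protocol's own cut-offs: 3 × ULN for ALT and AST, 2 × ULN for bilirubin, with the 1.5 × ULN entry limit as an optional lower band.
2. Count and list participants meeting the laboratory part of the Appendix 3 Section 6 combination, derived from the laboratory data, with jaundice taken from the adverse event data. State whether the two results must come from the same sample.
3. Apply the Appendix 4 HH/LL flags, or record their omission in SAP 3.3.
4. State which ULN applies, after reconciling protocol Appendix 4 with SAP 17.3 and 17.3.1.

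A special-interest row in the overall adverse event summary is optional. No clinical threshold changes, and no new samples or visits are needed. The cost is SAP wording, one table, one listing, the flags if retained, and a decision on the reference range before programming starts. The downside is a little programming for a table that may be mostly zeros.

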17.4. ECG EVALUATIONS

Results from the central ECG (Electrocardiogram) Reading Centre will be included in the reporting of this study.

The following ECG parameters will be reported for this study:

- PR Interval (msec)
- QRS Interval (msec)
- QT Interval (msec)
- QTc Interval (msec)
- QTcF Interval (msec)
- Pulse Rate (bpm)
- Overall assessment of ECG (Investigator's judgment):
 - Normal
 - Abnormal, Not Clinically Significant (ANCS)
 - Abnormal, Clinically Significant (ACS)
 - Not Evaluable

If triplicate ECG testing is done for this study, the latest test on the same visit will be used in the summaries.

The following summaries will be provided for ECG data:

- Actual and change from baseline by visit (for quantitative measurements)
- Overall Assessment by visit
- Shift from baseline to worst post-baseline by Overall Assessment

Document: Roche_YP40902_SAP

Authors: [REDACTED], [REDACTED], [REDACTED]

Version Number: 2.2

Version Date: 06MAR2020

Template No.: CS_TP_BS016 Revision 5

Reference: CS_WI_BS005

Effective Date: 01April2018

- The summary statistics for QTcF, number of subjects with value > 450, > 480 and > 500, change from baseline > 30, > 60 and > 90 will be summarized
- Listing of all ECG parameters

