### **8.2.3        Electrocardiograms**

- 12-lead ECGs will be obtained as outlined in the SoA (see [Section 1.3](#)) using an ECG machine that automatically calculates the pulse rate and measures PR, QRS, QT, and QTc intervals. *Triplet 12-lead ECGs can be performed at specified timepoints if deemed necessary by investigator.*
- At each timepoint at which triplicate ECGs are required, three individual ECG tracings should be obtained as closely as possible in succession, but no more than 2 minutes apart. The full set of triplicates should be completed in less than 4 minutes.
- To minimize variability, it is important that participants be in a resting position (for approximately  $\geq$  10 minutes) prior to each ECG evaluation. Body position should be consistently maintained for each ECG evaluation to prevent changes in heart rate. Environmental distractions (e.g., television, radio, conversation) should be avoided during the pre-ECG resting period and during ECG recording. Electrocardiogram should be performed prior to any scheduled vital sign measurements and blood draws. In some cases, it may be appropriate to repeat abnormal ECGs to rule out improper lead placement as contributing to the ECG abnormality.
- If at a particular postdose timepoint the mean QTcF is  $>$  500 ms and/or 60 ms longer than the baseline value, another triplicate ECG must be recorded, ideally within the next 5 minutes, and triplicate ECG monitoring should continue until QTcF has stabilized on two successive ECGs. The Medical Monitor should be notified. Standard-of-care treatment may be instituted per the discretion of the investigator. If a PK sample is not scheduled for that timepoint, an unscheduled PK sample should be obtained. The investigator should also evaluate the participant for potential concurrent risk factors (e.g., electrolyte abnormalities, co-medications known to prolong the QT interval, severe bradycardia).
- For safety monitoring purposes, the investigator or designee must review, sign, and date all ECG tracings. Paper or electronic copies will be kept as part of the participant's source documents at the study center.

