17.4.1. ECG MARKEDLY ABNORMAL CRITERIA

Markedly abnormal quantitative ECG measurements will be identified in accordance with the following predefined markedly abnormal criteria for worst post-baseline result:

- Absolute values for QTcF will be classified as:
 - > 450 msec
 - > 480 msec
 - > 500 msec
- Change from Baseline for QTcF will be classified as:
 - >30 msec increase from baseline
 - >60 msec increase from baseline

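### SAP 17.4 uses the latest test when triplicate ECGs are done, instead of the mean QTcF the protocol judges, and does not say how a triggered repeat set enters the QTcF counts

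*SAP*

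**What the plan says.** SAP 17.4 sets the rule for multiple tracings: "If triplicate ECG testing is done for this study, the latest test on the same visit will be used in the summaries". The outputs listed below it include change from baseline by visit, "Shift from baseline to worst post-baseline by Overall Assessment", and the QTcF counts ("number of subjects with value > 450, > 480 and > 500, change from baseline > 30", with further change cut-offs after that). SAP 17.4.1 then applies its "predefined markedly abnormal criteria for worst post-baseline result". Its cut-offs include >500 msec and ">60 msec increase from baseline".

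Protocol 8.2.3 works from the average. Its condition begins "If at a particular postdose timepoint the mean QTcF is" and continues with 500 ms and/or 60 ms above baseline. When the condition is met, a further triplicate is required within minutes. The protocol also says when such repeats may end: "triplicate ECG monitoring should continue until QTcF has stabilized on two successive ECGs".

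Three other rules bear on this:

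- Triplicates are at the investigator's discretion (protocol 8.2.3; Table 1, footnote f).
- SAP 6.5 limits its latest-value rule for retests to by-visit summaries. It keeps unscheduled measurements out of those summaries but lets them count towards best or worst values.
- SAP 6.4 takes the last pre-dose measurement as baseline unless something else is specified.

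**The concern.** Two things are unsatisfactory.

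First, the SAP does not average a triplicate. The protocol compares a mean with its limits, while the tables use the latest test. If that means the last tracing, two of three readings are set aside. If it means the last set, the SAP does not say how three readings become one value.

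Second, the standing of a repeat set is open. The protocol's trigger levels are the same 500 ms and 60 ms that the SAP uses as category limits, so a participant who triggers a repeat is the one the category table exists to show. The ECG rule covers the summaries without restriction. Taken literally, it would put the end of the repeat series in the table in place of the triggering set. SAP 17.4.1 and 6.5 point the other way. Two programmers could build different >500 or >60 ms tables from identical data.

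At stake is the accuracy of a descriptive safety table in which one participant is 1/16 = 6.25 percentage points of a dose group.

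**Working it through.** The documents give no figure on this point, so there is nothing to reproduce. The check compares the rules and then sizes the effect under stated assumptions.

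**Rules side by side**

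| Place | Value used | Scope |
|---|---|---|
| Protocol 8.2.3 | Mean QTcF at the timepoint | Real-time action |
| SAP 17.4 | Latest test, same visit | The summaries, no limit stated |
| SAP 17.4.1 | Worst post-baseline result | QTcF categories |
| SAP 6.5, retest | Latest value | By-visit summaries only |
| SAP 6.5, unscheduled | Not used by visit; counts towards worst value | Depends on the output |

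No section says which of the last two rows a triggered repeat set falls under, or whether the worst value is picked before or after the latest-test rule is applied.

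**Illustration.** Invented tracings of 512, 506 and 496 ms have mean (512 + 506 + 496)/3 = 504.7 ms, which is above 500. The latest tracing is 496 ms, which is not. On the last-tracing reading, the participant triggers the protocol action and is absent from the >500 count, even before any repeat set is considered.

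**False >30 ms counts with no drug effect**

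Inputs from the documents: 16 per group; seven post-dose ECG times in protocol Table 2 (2, 4, 12, 24, 48, 72 and 120 h). Assumptions, not in the documents: within-occasion SD w = 5-10 ms; between-occasion SD b = 8-12 ms; normal, independent errors.

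The SD of one change from baseline is √(2(b² + w²)) with single tracings at both ends and √(2(b² + w²/3)) with triplicate means at both ends. For b = 8, w = 10 these are √328 = 18.1 ms and √194.7 = 14.0 ms. A participant counts if the largest of the seven changes exceeds 30 ms. By simulation, expected participants per 16 if triplicates are done at baseline and all seven times:

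| b, w (ms) | Latest tracing | Triplicate mean | Difference |
|---|---|---|---|
| 8, 5 | 1.00 | 0.54 | 0.46 |
| 8, 10 | 3.20 | 1.22 | 1.98 |
| 10, 5 | 2.08 | 1.58 | 0.50 |
| 10, 10 | 4.09 | 2.32 | 1.77 |
| 12, 5 | 3.34 | 2.90 | 0.44 |
| 12, 10 | 5.03 | 3.54 | 1.49 |

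This is a ceiling of 0.4-2.0 fewer. Because triplicates are discretionary, a more realistic case is a single-tracing baseline and one triplicate post-dose time per participant. The gain is then 0.04-0.16 per 16, or 0.01-0.04 if a quarter of participants have one. The other six times and the baseline remain single tracings, so most of the noise is untouched.

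**Triggered case.** Suppose baseline and post-dose are both triplicates, the first set's mean change exceeds 60 ms and the true change is constant. That set's own last tracing, minus the last baseline tracing, still reads 60 ms or less in about 30% of cases at a true +60 ms and 19-25% at +65 ms. Using the last tracing of a repeat set instead, the figures are 41% and 22-31%. With no drug effect and the same SDs, the expected number of participants out of 32 with any triplicate-mean change above 60 ms is 0.0001-0.15.

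**The case against.** The strongest reply is that SAP 6.5 may already resolve the repeat-set question. Triggered repeats are not in the protocol's schedule tables. If they are recorded as unscheduled, the scheduled triggering set stays in the by-visit tables and both sets can supply the worst value. A reader might infer from SAP 17.4 that the triggering set is certainly lost. The documents do not support that: it follows only if the repeats share the visit and 17.4 overrides 6.5 and 17.4.1. What stands is that the SAP leaves the coding open. The output templates named in SAP 8 were not available and may settle part of it.

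It is also fair to say that a bedside action and a descriptive table need not use the same statistic, so this is not a contradiction between protocol and SAP. But the SAP gives no reason to prefer the latest test, and averaging costs almost nothing.

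Two wider readings also fail. A reader might infer that only the 12 h ECG on Day 1 survives, because the rule speaks of a visit. SAP 6.6 organises the data by scheduled time, so the wording is merely loose. A reader might also extend the criticism to laboratory retests. That latest-value rule is confined to by-visit summaries in SAP 6.5 and 17.3, and nothing removes superseded values from the worst-value tables.

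**Conclusion.** The point holds as a low-severity improvement to a stated rule. SAP 17.4 does not use the mean on which the protocol acts, and its unrestricted scope leaves the worst-case QTcF counts open to more than one reading.

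The effect is confined to descriptive safety tables. No tests are planned (SAP 6.7), ECG is not a named endpoint (protocol Table 3), all values are listed, and the Medical Monitor is notified of a triggered QTcF. If only single ECGs are recorded, there is no effect.

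The realistic gain in false >30 ms counts is about 0.04-0.16 participants per group of 16. A reader might take the 0.4-2.0 range as the expected gain, but it needs triplicates at every timepoint, which the protocol does not require. The triggered-case percentages are conditional on an event expected in at most about 0.15 of 32 participants without a drug effect. They show what could happen to one participant's category, not a likely bias. All these sizes rest on assumed SDs and, for the latest-test figures, on reading the latest test as the last tracing.

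**What to change.** Amend SAP 17.4 as follows:

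1. Where triplicates exist, use the mean of the evaluable tracings at each scheduled timepoint for quantitative parameters. Do the same for baseline; SAP 6.4 leaves room for such an exception.
2. Use the scheduled (first) set in by-timepoint summaries. Treat triggered repeat sets as unscheduled under SAP 6.5, so that every post-baseline set, each as its mean, counts in the QTcF category outputs of 17.4 and the worst post-baseline outputs of 17.4.1.
3. For the shift to worst Overall Assessment, use the worst evaluable assessment.
4. Refer to the scheduled timepoint, not the visit.

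The cost is SAP wording and minor programming. No new assessments are needed, and the protocol's monitoring rule is untouched. The drawback is that participants with repeat sets get more chances to cross a cut-off, so the category table should footnote how many participants had them.
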